1.2 Schema

Feasibility study Phase A (n=15 subjects)

Feasibility study Phase B (n=10-50 subjects)

LUMICELL COMPANY CONFIDENTIAL

This document is confidential. Do not disclose or use except as authorized.

1.3 Objectives

Primary objectives of the Feasibility Study:

(1) To determine the dose to be used in the pivotal trial; (2) to evaluate the detection algorithm for identifying residual cancer in the tumor bed; and (3) to gather additional safety data of the LUM Imaging System in breast cancer subjects.

2. BACKGROUND

2.1 LUM Imaging System

The Luminicell imaging system is a combination product consisting of an imaging device and an imaging agent (LUM015).

2.1.1 LUM Imaging Device

The LUM Imaging Device consists of a computer control unit, monitor and light source mounted in a cart, and a hand-held imaging head (LUM 2.6 imaging head). The computer control unit collects, analyzes (based upon Luminicell's detection algorithm) and displays the resulting images gathered by the imaging head in real-time. The light source provides the illumination to excite the fluorescent dye present in LUM015. Light is transferred from the light source to the imaging head using an optical fiber bundle. The imaging head (**Figure 3**) was designed as a lightweight hand-held tool with a small profile to allow easy maneuverability and limited intrusiveness into the operating room. The imaging head has a 45° bend at the distal end for examination of the walls of the lumpectomy cavity.

The hand-held optical head will be used within the sterile surgical field. Consequently, a sterile barrier assembly will be used to cover the optical head, which comes into contact with both the surgeon and the patient's exposed tumor bed. The sterile barrier assembly consists of a pre-assembled 1) sterile, disposable optical window made of plastic with a glass insert, which maintains the imaged tissue at the focal plane of the imaging system and 2) sterile, disposable plastic drape (510(k) clearance number K964142). The disposable optical window and drape are installed on the LUM Optical Head in the OR following aseptic procedures just prior to the imaging procedures.

Luminicell's intraoperative imaging approach consists of several steps: (1) acquire wide field of view image with microscopic resolution; (2) identify abnormal tissue using a computational algorithm; and (3) provide feedback to the surgeon by displaying the location of the abnormal tissue in an image (monitor) or indicating that the image of the zone does not have a positive indication of cancer tissue. Most importantly, all these steps are accomplished in real-time.

Figure 3: (Left) Photo of the LUM 2.6 imaging head. (Right) Rendering of the LUM hand-held imaging head scanning a lumpectomy cavity. The sterile transducer cover over the device is not shown.

The LUM 2.6 imaging head is powered by Luminell's proprietary detection software which processes the fluorescence images, determines whether any tumor margin cells are in the field of view and highlights them. The software performs corrections for camera dark counts and uneven illumination to improve performance across the entire field of view. The software uses images of normal tissue to set the threshold to identify normal from abnormal tissue. When the surgeon scans the tumor bed, the detection software compares the intensity of an image against the threshold and identifies whether a region of the image contains abnormal tissue. Regions with signal above the threshold are displayed as highlighted regions on the monitor. Figure 3 shows an image of actual residual cancer (**Figure 4a** and **b**) along with what the surgeon sees (**Figure 4c**) in real-time with Luminell's algorithm indicating the regions with residual cancer to be removed. The algorithm was developed based upon hundreds of tissue images from mice, dogs and humans compared against pathology of the imaged tissue. Based on a typical image size of ~6 Mbytes and a transfer rate of 10 Hz, the nominal requirements for the computer are: 2.0 GHz processor, 512 Mbytes of RAM, and operates in a Windows environment. The image acquisition and analysis software is written in C++.

[figure not shown]

Figure 4: (a) A fluorescence image is shown that was taken from a mouse-sarcoma tumor bed after surgery in a mouse following IV injection of LUM015. (b) The same image was analyzed by Luminell's detection system and regions containing residual cancer are highlighted in red. (c) This panel shows the user interface that the surgeon will see.

2.1.2 LUM015

LUMICELL COMPANY CONFIDENTIAL

This document is confidential. Do not disclose or use except as authorized.

Lumicell engineered LUM015, a fluorescence-based imaging agent that accumulates within the tumor and the tumor invasive front and is activated by cathepsin enzymes at these locations to label regions that should be removed during surgery. In its native state, the fluorescence of LUM015 is suppressed by an internal quencher molecule (QSY21); however, once cathepsin proteases cleave LUM015 at its amino acid backbone, the quencher is released and the fluorescent dye Cy5 in LUM015 emits detectable fluorescence (**Figure 5**). The absorption and emission wavelength maxima for the fluorescent molecule used, Cy5, are 649 nm and 670 nm respectively. LUM015 employs a fluorescent molecule with excitation and emission in the far red spectrum (< 700 nm wavelength) because in that range light can travel effectively through 1mm of tissue and tissue autofluorescence is minimal, allowing higher sensitivity due to lower background [2].

[figure not shown]

Figure 5: Schematic representation of LUM015.

Cathepsins are a family of enzymes that are involved with the degradation of the extracellular matrix to allow tumor growth and progression. These enzymes are upregulated in most human cancers and are also present in tumor associated macrophages at the invasive front [3-7]. Platt et. al. shows 60-fold higher cathepsin activity in breast cancer tissue than in healthy breast tissue [8]. Others report over-expression of cathepsin enzymes (B, K, L and D) in ductal carcinoma in situ as well as in invasive carcinomas (lobular and ductal) [4, 8-11]. Also, cathepsin B is typically over-expressed in inflammatory breast cancer, the most lethal form of primary breast cancer with a 3-year survival rate of 40% [12, 13]. The peptide sequence used in LUM015 is a pan-cathepsin substrate meaning that it will be cleaved by multiple enzymes of the cathepsin family. Because high activity of cathepsin enzymes is found in tumor cells and tumor associated macrophages surrounding the tumor at the invasive front, these enzymes provide an excellent marker for activating LUM015 at the tumor margin. The fluorescence of LUM015 is then detected with the LUM Imaging System to identify cancer and cancer-related cells from adjacent normal tissue.

Lumicell's imaging agent application is unique as its properties allow the detection of cancer cells at or just below the surface of the exposed tumor bed to be consistent with the margin assessment performed by pathology. For this protocol, positive margins are declared when cancer cells are present at the inked surface.

The safety of LUM015 has been investigated under IND 111,670, in a study titled: "A Phase 1 Study of the Safety and Activation of a Cathepsin-activatable Fluorescent

LUMICELL COMPANY CONFIDENTIAL

This document is confidential. Do not disclose or use except as authorized.

Cancer Specific Probe LUM015.” The IND Sponsor is [name], PhD, Associate Professor of Radiation Oncology at Duke University School of Medicine where the study was being conducted. The device component of the system was not used on subjects in the Phase I study, but was used to image excised tissue in the pathology suite. No clinical treatment decisions were made on the basis of this imaging during the Phase 1 study.

The Phase I study has been completed with fifteen subjects participating in the trial (see Table 2 below for a summary of the study cohorts) under the IND 111670. No adverse pharmacological activity (APA) or adverse events were observed in any of the subjects. Tissues from these subjects were imaged ex vivo using Lumicell’s current device and we determined an average tumor signal to background (normal tissue) signal ratio (TBR) of 5:1 (Table 3).

Table 2: Summary of the Phase I study cohorts.

Cohort	Number of patients	Dose (mg/kg)	Imaging time point (hr)
1	3	0.5	~29
2a	3	1.0	~29
2b	3 (1 breast cancer subject)	1.0	~6
3	3 (1 breast cancer subject)	1.5	~6
4	3 (1 breast cancer subject)	0.5	~6

2.1.3 Use of the LUM Imaging System

LUM015 is reconstituted in 0.45% saline at the institution’s pharmacy prior to the injection and is stable for 4 hours when stored at room temperature or 24 hours when stored refrigerated between 2°C and 8°C. Following the instructions for use, a calculated amount of solution volume of LUM015 is obtained based on the dose and the patient’s most recently obtained body weight and placed in a sterile syringe. LUM015 is administered into the patient via slow intra-venous push 2 to 6 hours prior to the surgery.

Prior to starting the surgery, the LUM Imaging Device will be located at the operating room and powering up routines and calibrations will be performed by OR personnel according to the instructions for use (IFU). A sterile imaging tip and drape will be installed over the device to provide a barrier between the imaging head and the sterile field. During surgery, once the surgeon removes the bulk tumor mass, the surgeon will place the LUM Imaging Head in contact with normal appearing tissue within the surgical incision to obtain a fluorescence baseline. Then, the surgeon will scan the tumor bed cavity. Real-time images are displayed in gray-scale and regions with residual fluorescence identified as abnormal tissue by Lumicell’s detection algorithm will be highlighted in red in the screen (**Figure 4**). The surgeon will then take shavings from the tumor bed cavity regions indicated to contain abnormal tissue.

Final margin assessment by a pathologist is conducted based on the last shavings removed.

To date, the intraoperative imaging system has been tested in mice and dogs and post-surgery in humans and achieved superb sensitivity and specificity across these species and several cancer types as shown in Table 3. We define sensitivity and specificity when imaging is compared against pathology of the imaged tissue.

Table 3: Luminicell's technology has high sensitivity and specificity across cancers and species.

Species and cancer type	Endpoint	Sensitivity and Specificity	Tumor-to-normal tissue signal ratio
Humans (60 tissue samples)	Pathology of resected tissue	100%, 71%	5:1
Dogs with lung, mammary gland, sarcoma, mast cell tumors (96 tissue samples for 21 subjects)	Pathology of resected tissue and negative margins	93%, 95%	7:1
Mice with sarcoma (n=105)	Pathology of resected tissue	90%, 80%	8:1
Mice with sarcoma (n=34)	Local recurrence	80%, 80%	8:1
Mice with breast cancer (n=44)	Pathology of resected tissue	100%, 100%	8:1

2.2 Study Disease

We propose to conduct a clinical trial to test the performance of the LUM Imaging System during breast tumor resection to ensure that negative margins are obtained during the initial surgery thus eliminating the need for a second resection. For breast cancer lumpectomies, the presence of residual cancer cells left in the tumor bed after initial resection is inferred by post-operative margin assessment of the resected tissue by a pathologist. If tumor cells are found near or at the edge of the resected tissue, the patient is considered to have close or positive margins. Positive lumpectomy margins are the most important risk factor for local recurrence [14-16] and dictate that a second surgical procedure is required. Rates of close or positive margins have been reported in the range between 17 to 59% [17-21]. In two separate retrospective reviews of lumpectomies performed at the Massachusetts General Hospital between 1997 and 2007, we found rates for close or positive margins of 23% [22] and 36% [23]. Our review also found that 91% of patients with positive margins had re-excision surgeries followed by adjuvant radiation therapy. Furthermore, approximately 32% of patients having either one or two re-excisions still had close or positive margins. We estimate that in the US more than 150,000 women undergo lumpectomy for breast cancer each year and approximately a third of them require additional surgery for positive margins. Thus, a diagnosis of

positive margins indicates that additional treatments are needed which places a heavy burden on patients and may be a large added cost to the healthcare system.

2.3 Rationale

Detection of negative margins during tumor excision is critical to assure all the cancer has been removed from the tumor bed. Current standard of care dictates that tissue removed during surgery is analyzed post-operative by a pathologist as described above. This procedure is time consuming, often requiring 7-10 days of pathological testing after the operation before margin status is known. In addition, this process is prone to sampling errors as only a finite number of tissue slices can be examined. Thus, a safe method to directly assess the entire tumor bed and identify residual microscopic disease for resection intraoperatively would be highly beneficial for patients.

Lumicell has developed the LUM Imaging System, a fluorescence-based imaging agent and a hand-held, wide-field detector that can image the lumpectomy cavity in seconds to identify microscopic residual disease. The technology has demonstrated single cell detection and is insensitive to the natural motions of the surgeon or the patient. Therefore, this technology may enable surgeons to achieve negative margins during the initial surgery and eliminate the need for re-excision surgeries. The detection system images the tumor bed, overcoming tissue handling and sampling limitations of standard pathology analysis of resected tissue. The LUM imaging head is compact, provides real-time feedback to the surgeon about the status of the tumor bed, and does not require patient immobilization; hence, the technology does not have a significant impact on the surgical workflow. With this technology, breast cancer surgeons can make decisions that have the potential to prevent repeat surgeries, minimize patient discomfort, and reduce surgical risks.

Lumicell has demonstrated safety and efficacy in over 100 mice and 21 dogs (currently running a clinical trial in canine subjects at Tufts University Cummings School of Veterinary Medicine with [name] and the Veterinary Specialty Hospital of the Carolinas with [name]).

The current protocol describes a clinical trial to evaluate the efficacy of the LUM Imaging System in achieving negative margins in breast cancer subjects. In the initial feasibility study, we will finalize the algorithm used in the LUM Imaging System to detect residual cancer when compared against histology. In subjects from the Pivotal Study, we will prospectively evaluate the efficacy of the technology to detect residual cancer and reduce the rates of post-operative positive margins.

2.4 Correlative Studies Background

Not applicable.

3. SUBJECT SELECTION

3.1 Eligibility Criteria

Subjects must meet the following criteria on screening examination to be eligible to participate in the study:

- 3.1.1 Subjects must have histologically or cytologically confirmed primary breast cancer. The methods for obtaining the histological samples can include diagnostic biopsies, core needle biopsies or fine needle biopsies.
- 3.1.2 Female, age of 18 years or older. Because no dosing or adverse event data are currently available on the use of LUM015 in subjects <18 years of age, children are excluded from this study.
- 3.1.3 Subjects must be scheduled for a lumpectomy of a breast malignancy.
- 3.1.4 Subjects must be able and willing to follow study procedures and instructions.
- 3.1.5 Subjects must have received and signed an informed consent form.
- 3.1.6 Subjects must be otherwise healthy except for the diagnosis of cancer, as per the exclusion criteria listed below.
- 3.1.7 Subjects must have normal organ and marrow function as defined below:
 - Leukocytes \geq 3,000/mcL
 - Platelets \geq 100,000/mcL
 - total bilirubin within normal institutional limits
 - AST (SGOT)/ALT (SGPT) \leq 2.5 X institutional upper limit of normal
 - Creatinine \leq 1.5 mg/dL or creatinine clearance \geq 60 mL/min/1.73 m² for subjects with creatinine levels above institutional normal.
- 3.1.8 The effects of LUM015 on the developing human fetus are unknown. For this reason, women of child-bearing potential must agree to use adequate contraception (hormonal or barrier method of birth control, abstinence) starting the day entering the study, and for 60 days after injection of the imaging agent. Should a woman become pregnant or suspect she is pregnant while participating in this study, she should inform her treating physician immediately. Breast cancer patients are routinely advised against pregnancy during treatment, so this requirement does not differ from standard of care.
- 3.1.9 Subjects with ECOG performance status of 0 or 1.

3.2 Exclusion Criteria

LUMICELL COMPANY CONFIDENTIAL
This document is confidential. Do not disclose or use except as authorized.

Subjects who exhibit any of the following conditions at screening will not be eligible for admission into the study.

- 3.2.1 Subjects with a known current condition of substance addiction.
- 3.2.2 Subjects who have taken an investigational drug within 30 days of enrollment.
- 3.2.3 Subjects with prolonged QT interval.
- 3.2.4 Subjects who will have administration of methylene blue or any blue dye used for sentinel node mapping procedures prior to imaging the lumpectomy cavity with the LUM 2.6 Imaging Device.
- 3.2.5 Subjects who have not recovered from adverse events due to pharmaceutical or diagnostic agents.
- 3.2.6 Subjects with uncontrolled hypertension defined as persistent systolic blood pressure > 150 mm Hg, or diastolic blood pressure > 95 mm Hg; those subjects with known HTN should be stable within these ranges while under pharmaceutical therapy.
- 3.2.7 Subjects with insulin dependent diabetes mellitus.
- 3.2.8 History of anaphylactic reaction attributed to any contrast agent or drugs containing polyethylene glycol (PEG).
- 3.2.9 Uncontrolled intercurrent illness including, but not limited to ongoing or active infection, symptomatic congestive heart failure, unstable angina pectoris, cardiac arrhythmia, COPD or asthma requiring hospitalization within the past 12 months, or psychiatric illness/social situations that would limit compliance with study requirements.
- 3.2.10 Pregnant women are excluded from this study because the teratogenic properties of LUM015 are unknown. Because there is an unknown but potential risk of adverse events in nursing infants secondary to treatment of the mother with LUM015, breastfeeding should be discontinued if the mother is treated with LUM015. These potential risks may also apply to other agents used in this study.
- 3.2.11 Subjects who are sexually active and not willing/able to use medically acceptable forms of contraception upon entering the study; this exclusion is necessary because the teratogenic properties of the study imaging agent are unknown.
- 3.2.12 HIV-positive individuals on combination antiretroviral therapy are ineligible because of the potential for pharmacokinetic interactions with LUM015.
- 3.2.13 Any subject for whom the investigator feels participation is not in the best interest of the subject.
- 3.2.14 Subjects undergoing a second surgery because they had positive margins in a previous surgery.
- 3.2.15 Subjects with prior ipsilateral breast surgeries, mastectomies, breast reconstructions or implants. (Note: subjects who have had prior breast biopsies are not excluded; see inclusion criterion 3.1.1.)
- 3.2.16 Subjects with prior ipsilateral reduction mammoplasties or breast reductions performed less than 2 years prior to enrollment to this study.

LUMICELL COMPANY CONFIDENTIAL

This document is confidential. Do not disclose or use except as authorized.

3.2.17 Subjects previously treated with systemic therapies to treat the cancer to be removed during this clinical investigation, such as neo-adjuvant chemotherapy or hormonal therapy.

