4. SUBJECT ENROLLMENT

4.1 General Guidelines for Screening and Enrollment

The Institution will register eligible participants with the DF/HCC Quality Assurance Office for Clinical Trials (QACT) central registration system. Registration must occur prior to the initiation of therapy. Any participant not registered to the protocol before treatment begins will be considered ineligible and registration will be denied.

An investigator will confirm eligibility criteria and a member of the study team will complete the QACT protocol-specific eligibility checklist.

Following registration, participants may begin protocol treatment. Issues that would cause treatment delays should be discussed with the Principal Investigator. If a participant does not receive protocol therapy following registration, the participant's protocol status must be changed. Notify the QACT Registrar of participant status changes as soon as possible.

The study team will document subject eligibility on the Screening and Enrollment form and notify Luminell of a potential candidate for the study after the subject has been consented.

The subject is not considered enrolled into the study until written Informed Consent is obtained and the investigational product has been administered (Study Day One).

Luminell will perform an analysis of the data collected in Arms 1 and 2 to determine if the acceptance criterion is met (normal tissue signal is separated by 4 standard deviations from the mean autofluorescence in normal tissue) and an additional 5 subjects (Feasibility Study Phase A, Arm 3) will be enrolled in the study if the acceptance criterion is not met. Luminell will notify the clinical site when enrollment can restart.

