8. STUDY CALENDAR

Baseline evaluations are to be conducted within 4-weeks prior to subject enrollment. All baseline assessments must be performed prior to administration of any study agent. All study assessments should be administered within \pm 3 days of the protocol-specified date, unless otherwise noted. The study calendar below applies to the initial five subjects that are not injected with LUM015 and all subjects injected with LUM015 including those that do not undergo imaging due to a failure in the LUM 2.6 Imaging Device initialization.

	Pre- Enrollment /Screening	Day 1 / Enrollment	2-14 days after surgery	Routine follow up visit
LUM015 administration		X		
Informed consent	X			
History	X			
Concurrent meds	X			
Physical exam (Ht, Wt, BSA, VS)	X			
Surgery/intraoperative imaging		X		
Margin assessment			X	
CBC	X			X
EKG	X			
Serum chemistry ^a	X			X
Adverse event/adverse device effect evaluation		X		X
Tumor measurements	X		X	
Radiologic evaluation	X			
B-HCG	X ^b			

a: Albumin, alkaline phosphatase, total bilirubin, BUN, calcium, chloride, glucose, potassium, total protein, SGOT [AST], SGPT [ALT], sodium.

b: Serum pregnancy test (women of childbearing potential).

LUMICELL COMPANY CONFIDENTIAL

This document is confidential. Do not disclose or use except as authorized.

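### No re-verification of eligibility, including pregnancy status, is scheduled between screening (up to 28 days earlier) and the single LUM015 injection

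*Combined protocol and SAP*

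**What the plan says.** Both criteria lists are anchored to screening. Section 3.1 opens with "Subjects must meet the following criteria on screening examination to be eligible to participate in the study" and Section 3.2 with "Subjects who exhibit any of the following conditions at screening will not be eligible for admission into the study".

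Section 8 sets the window and the order: "Baseline evaluations are to be conducted within 4-weeks prior to subject enrollment" and "All baseline assessments must be performed prior to administration of any study agent". Section 4.1 fixes when the window closes: a subject does not count as enrolled "until written Informed Consent is obtained and the investigational product has been administered (Study Day One".

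On pregnancy, item 3.2.10 states: "Pregnant women are excluded from this study because the teratogenic properties of LUM015 are unknown". Item 3.1.8 requires contraception from women of child-bearing potential "starting the day entering the study, and for 60 days after injection of the imaging agent", and asks a woman who is or may be pregnant to tell her physician at once. Item 3.2.11 excludes "Subjects who are sexually active and not willing/able to use medically acceptable forms of contraception upon entering the study".

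Section 5.7 makes discontinuation mandatory on pregnancy and provides for replacing subjects removed before dosing. Section 5.5 lets the investigator discontinue a subject for safety or because her condition has changed.

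**The concern.** LUM015 is given once, so the last useful moment to detect an exclusion is just before the injection. The protocol excludes pregnancy because effects on the fetus are unknown, yet the test that enforces this may be four weeks old when the agent is given. A woman can be correctly screened as not pregnant, conceive during the interval, and reach Day 1 with nothing scheduled that would reveal it. Other exclusions that can arise within weeks, such as an active infection (3.2.9), blood pressure outside the stated limits (3.2.6) or an adverse event not yet resolved (3.2.5), are in the same position, although visible illness is more likely to be noticed.

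At stake is an avoidable and irreversible exposure of the kind 3.2.10 is written to prevent. Phase A is complete, so the point bears on Phase B, where up to 50 subjects are to be injected.

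**Working it through.** No statistical figure is involved. The check sets the sections side by side.

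1. **When criteria are judged.** At screening, for both lists (3.1, 3.2).
2. **Length of the window.** 4 weeks × 7 days = 28 days before enrollment (Section 8).
3. **Where the window ends.** Enrollment requires that the product has been given (4.1), so the window runs up to the injection. The gap between the baseline tests and the injection is therefore anything up to 28 days. The rule that baseline assessments precede the agent fixes their order, not how recent they must be.
4. **What the Section 8 calendar schedules.**

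| Assessment | Screening | Day 1 |
|---|---|---|
| Serum B-HCG | yes | no |
| History | yes | no |
| Physical exam and vital signs | yes | no |
| EKG | yes | no |
| CBC, serum chemistry | yes | no (next at routine follow-up) |
| Concurrent medications | yes | no (but see 5.4) |
| LUM015, surgery/imaging, adverse event evaluation | no (none of the three) | yes (all three) |

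   Scheduled pregnancy tests after screening and before injection: 0.

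5. **Whether another section closes the gap.**
   - 5.1 sets no pre-dose condition.
   - 4.1 and 4.2 have an investigator confirm eligibility and the registrar validate it before treatment. The checklist is completed from the assessment already in the record, and registration is not tied to Day 1. The screening result is carried forward.
   - 5.4 updates medications at enrollment as needed. This is a real check near dosing, but it covers medications only.
   - 5.5 and 5.7 say what follows once a change is known. Neither schedules anything to find it. Before injection, the information must come from the subject herself (3.1.8) or from incidental discovery.

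6. **When contraception starts.** Item 3.1.8 refers to the day of entering the study, a term that is not defined.
   - If entry means consent or screening, the interval is covered, because 4.2 places consent before any study procedure and hence before the pregnancy test.
   - If entry means enrollment as defined in 4.1, it is Day One, and up to 28 days between test and injection are uncovered.

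   The text does not settle which is meant.

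7. **Scope of the two contraception criteria.** Item 3.1.8 applies to women of child-bearing potential; 3.2.11 applies to any sexually active subject. Read literally, 3.2.11 also excludes a post-menopausal, sexually active woman who uses no contraception, whom 3.1.8 would not affect.

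**The case against.** The strongest reply is that the plan already has safeguards. A reader might infer from the screening-only wording that a woman pregnant on Day 1 would be injected in accordance with the plan. The documents do not support that: 5.7 makes discontinuation mandatory, removal before dosing is foreseen, and injecting a woman known to be pregnant would breach the protocol. A reader might equally infer that eligibility is never looked at again. That is also too strong, given the confirmation at registration and the medication update. Nor is every criterion frozen at screening: 3.2.2, on recent investigational drugs, counts from enrollment and so already reaches Day 1.

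It can also be said that 3.1.8 names study entry and injection as two separate points, which fits entry at consent at least as well as entry on Day One, and that the protocol describes these patients as routinely advised against pregnancy. Both are fair. They make the contraception point an ambiguity, not a demonstrated gap in cover.

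What remains after these concessions is that none of the safeguards schedules a procedure that would reveal a change since screening. They govern the response to a known change, or they repeat a documented result.

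**Conclusion.** The point holds in this form: no re-verification of eligibility, including pregnancy status, is scheduled between a screening that may be 28 days old and the single injection, so before dosing the mandatory pregnancy rule rests on self-report or chance. This follows directly from Sections 3.1, 3.2, 4.1, 4.2, 5.7 and 8. The separate point on 3.1.8 is that contraceptive cover during the interval is undefined, not that it is absent.

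The size that the text supports is the interval, up to 28 days, with 0 scheduled pregnancy tests in it. It is tempting to lengthen the interval by the ±3-day allowance in Section 8, but that allowance attaches to a protocol-specified date, and the text does not extend it to the 4-week window. It is also tempting to estimate a number of exposed pregnancies. The documents give neither the share of women of child-bearing potential, nor the actual screening-to-injection times, nor any conception rate, so such a count would be assumption throughout. The event is probably rare. The case for change rests on the exposure being irreversible and the remedy being cheap. The efficacy analysis is not affected.

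**What to change.** (a) Reword the openings of 3.1 and 3.2 so that eligibility must still hold before LUM015 is injected. Add to Section 8 a Day 1 pre-injection confirmation of the criteria that can change, based on an interval history and the medication update that 5.4 already provides for.

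(b) Keep the single serum B-HCG, but tie its timing to the injection instead of allowing it anywhere in the 4-week window. The exact interval is for the sponsor to set.

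(c) Define study entry in 3.1.8 so that it is consistent with 4.1 and the contraception requirement covers the time between the pregnancy test and the injection.

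(d) Reconcile the differing scope of 3.1.8 and 3.2.11. Which population is intended is the sponsor's decision.

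The cost is protocol wording, one calendar entry and a short confirmation on Day 1, when the patient already attends for an injection 2 to 6 hours before surgery. No additional test is needed if the existing one is re-timed. The downside is an occasional screen failure on the day of surgery; 5.7 already provides for replacing subjects removed before dosing.
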